#### 5.5 **Definition of Dose-Limiting Toxicity (DLT)**

DLT will be defined as any of the following events that are possibly, probably or definitely attributable to protocol therapy. The DLT observation period for the purposes of dose-escalation will be the first cycle of therapy.

Dose limiting hematological and non-hematological toxicities are defined differently.

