#### 5.5.2 Hematological dose limiting toxicity

- 5.5.2.1 In patients evaluable for hematological toxicity (see Section 4.1.7.1), hematological dose limiting toxicity is defined as:
  - Day 15:
    - Grade 4 neutropenia or Grade 3 thrombocytopenia (platelets  $< 50,000/\text{mm}^3$ ) that does not resolve to ANC  $\ge 500/\text{mm}^3$  and platelets  $\ge 50,000/\text{mm}^3$  (transfusion independent) by Day 18 will be considered dose-limiting (See Section 6.1).
  - Grade 4 neutropenia for > 7 days
  - Platelet count < 20,000/mm^3 on 2 separate days, or requiring a platelet transfusion on 2 separate days, within a 7-day period
  - Myelosuppression that causes a delay of > 14 days between treatment cycles.
- 5.5.2.2 Note: Grade 3 or 4 febrile neutropenia will not be considered a doselimiting toxicity.

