#### 6.0 **DOSE MODIFICATIONS FOR ADVERSE EVENTS**

#### The Study Chair must be notified of any dosage modification or use of myeloid growth factor.

#### 6.1 **Dose Modifications for Day 15 Dosing due to Toxicity on Day 15**

#### 6.1.1 Hematologic Toxicity

- 6.1.1.1 Patients who have Grade 4 neutropenia or Grade 3 thrombocytopenia (platelets < 50,000/mm^3) on Day 15 will have their dose withheld. If the toxicity resolves to ANC  $\geq$  500/mm^3 and platelets  $\geq$  50,000/mm^3 (transfusion independent) by Day 18, the dose may be given. If the toxicity does not resolve to ANC  $\geq$  500/mm^3 and platelets  $\geq$  50,000/mm^3 by Day 18, the dose will be omitted and this will be considered a DLT. Patients should receive subsequent cycles of drug per Section 6.2. Patients who require that their Day 15 dose be omitted for Grade 4 neutropenia or Grade 3 platelets (< 50,000/mm^3) after two dose reductions must be removed from protocol therapy.
- 6.1.1.2 Patients who meet hematological DLT criteria as defined in Section 5.5.2.1 on Day 15 will have their Day 15 dose omitted. Patients should receive subsequent cycles of drug per Section 6.2 after their toxicity resolves, no sooner than the planned start of the subsequent cycle. Patients

nstitute of the National Institutes of Health

who require that their Day 15 dose be omitted for hematologic DLT as defined in Section 5.5.2.1 after two dose reductions must be removed from protocol therapy.

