#### 8.0 EVALUATIONS/MATERIAL AND DATA TO BE ACCESSIONED

#### 8.1 Required Clinical, Laboratory and Disease Evaluation

All clinical and laboratory studies to determine eligibility must be performed within 7 days prior to enrollment unless otherwise indicated. Laboratory values used to assess eligibility (see Section 4.0) must be no older than seven (7) days at the start of therapy. Laboratory tests need **not** be repeated if therapy starts **within** seven (7) days of obtaining labs to assess eligibility. If a post-enrollment lab value is outside the limits of eligibility, or laboratory values are older than 7 days, then the following laboratory evaluations must be re-checked within 48 hours prior to initiating therapy: CBC with differential, bilirubin, ALT (SGPT) and serum creatinine. If the recheck is outside the limits of eligibility, the patient may not receive protocol therapy and will be considered off protocol therapy. Imaging studies, bone marrow aspirate and/or biopsy, must be obtained within 14 days prior to start of protocol therapy (repeat the tumor imaging if necessary).

STUDIES TO BE OBTAINED	Pre- Study	During Cycle 1	Prior to Subsequent Cycles^
History	Х	Weekly	Х
Physical Exam with vital signs	Х	Weekly	Х
Neurologic Exam	Х		Х
Height, weight, BSA	Х		Х
Performance Status	Х		
CBC, differential, platelets	Х	Twice Weekly	Weekly 
_		(every 3 to 4 days) 	
Pharmacokinetics 	Х	X	
Electrolytes including Ca 2+ , PO 4  , Mg 2+	Х	Weekly	Х
Creatinine, ALT, bilirubin	Х	Weekly	Х
Albumin	Х		Х
Tumor Disease Evaluation	X	End of Cycle 1	Every other cycle x 2 then q 3 cycles 
Bone Marrow Evaluation 	X	X	Every other cycle x 2 then q 3 cycles 
Pregnancy Test 	Х		
ECHO or gated radionuclide study	Х		
EKG 	Х	X	X 
Tumor Tissue Submission 	Х		
Correlative Biology Studies (optional) 	Х	X	

Institute of the Natio

THIS PROTOCOL IS FOR RESEARCH PURPOSES ONLY, SEE PAGE 1 FOR USAGE POLICY

- Studies may be obtained within 72 hours prior to the start of the subsequent cycle, unless otherwise specified within the table.
- 1 See Section 8.3 for timing and details of pharmacokinetic (PK) studies.

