- 2 Women of childbearing potential require a negative pregnancy test prior to starting treatment; sexually active patients must use an acceptable method of birth control during the study and for 3 months after participation in this study. Abstinence is an acceptable method of birth control.
- 3 If patients have Grade 4 neutropenia then CBCs should be checked at least every other day until recovery to Grade 3 or until meeting the criteria for dose-limiting toxicity.
- 4 If patients develop Grade 4 neutropenia then CBCs should be checked every 3 to 4 days until recovery to Grade 3
- 5 Tumor Disease Evaluation should be obtained on the next consecutive cycle after initial documentation of either a PR or CR. Subsequent scans may restart 2 cycles after the confirmatory scan. Please note that for solid tumor patients, if the institutional investigator determines that the patient has progressed based on clinical or laboratory evidence, he/she may opt not to confirm this finding radiographically.
- 6 If a solid tumor patient is suspected to have or has a history of bone marrow involvement then a prestudy bone marrow biopsy and/or aspirate is required. This should then be repeated with each tumor disease evaluation.
- 7 See Section 8.4 for details regarding tumor tissue submission for the required and optional studies. If tissue blocks or slides are unavailable, the study chair must be notified prior to study enrollment.
- 8 See Section 8.5 for timing and details regarding correlative biology studies.
- 9 EKGs to be performed at baseline, and then immediately prior to and one hour after each infusion of LY2606368 is complete for the first 2 cycles. For subsequent cycles, EKGs are to be obtained as clinically indicated.

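### Extra Cycle 1 CBCs are triggered only by Grade 4 neutropenia, so whether a 2- to 6-day platelet nadir counts as a DLT depends on how often the site draws

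*Combined protocol and SAP*

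**What the plan says.** - **Platelet DLT (Section 5.5.2.1).** A platelet count below 20,000/mm³ qualifies if it occurs "on 2 separate days, or requiring a platelet transfusion on 2 separate days, within a 7-day period". There are thus two routes, one by counts and one by transfusions.
- **When it counts (Section 5.5).** "The DLT observation period for the purposes of dose-escalation will be the first cycle of therapy".
- **Required draws (Section 8.1, evaluation table).** CBC with differential and platelets is one line of the table. In Cycle 1 it is twice weekly, "every 3 to 4 days"; in later cycles it is weekly.
- **When draws become more frequent (Section 8.1, footnote 3).** "If patients have Grade 4 neutropenia then CBCs should be checked at least every other day until recovery to Grade 3", or until the DLT criteria are met. Footnote 4 gives a looser version for later cycles, again for neutropenia only.
- **Day 15 rule (Section 6.1.1.1).** A dose withheld for low counts may be given if counts recover by Day 18. If they do not recover "by Day 18, the dose will be omitted and this will be considered a DLT".
- **Use of the DLT count (Section 11.3).** Two or more DLTs in a cohort of up to six mean that the MTD has been exceeded, apart from the exception in Section 11.2.2.

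**The concern.** The count route needs two separate low values, so it can be met only if two draws fall inside the low period. For neutropenia the plan ties sampling to its duration-based DLT: footnote 3 keeps the draws close together until recovery or DLT. The platelet DLT also depends on duration but has no such rule.

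Two sites can therefore follow the protocol exactly and classify the same child differently. One draws at the minimum and sees a single low value; the other draws daily and records a DLT. The error at the minimum schedule goes one way: DLTs are missed and never added, which favours escalation. Because two DLTs in six stop escalation, one missed event can change the decision. A count that was never drawn cannot be recovered at later review.

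**Working it through.** The plan states no detection probability for this DLT, so there is no figure to reproduce.

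**Inputs from the documents.** The DLT needs 2 days within 7 (Section 5.5.2.1). Cycle 1 draws are twice weekly at 3- to 4-day gaps (Section 8.1). In adults at 105 mg/m², Grade 4 neutropenia was 66% and Grade 4 thrombocytopenia 6% (Section 2.3.1).

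**Assumptions.** Platelets stay below 20,000/mm³ for D consecutive days, with D from 2 to 7 because the documents give no duration. Onset is equally likely on any day of the week. There are no extra draws, and transfusion does not change the counts.

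**Step 1. Minimum schedule.** Put the draws on days 0 and 3 of each week, so the gaps alternate between 3 and 4 days. Two draws 3 days apart fit inside a run of D days for D − 3 of the 7 start days. Two draws 4 days apart fit for D − 4. No start is counted twice until D = 8. For D = 4 to 7 the share caught is therefore [(D − 3) + (D − 4)]/7 = (2D − 7)/7. Below D = 4 it is 0.

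**Step 2. Every-other-day repeats triggered by the first low value.** A repeat comes 2 days after the first scheduled draw that falls in the episode. The episode is caught if that first draw comes no later than D − 3 days after onset. Counting start days gives 0, 2, 4, 6, 7 and 7 of 7 for D = 2 to 7.

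**Step 3. Daily draws.** Every episode of 2 days or longer is caught.

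| Days below 20,000/mm³ | Minimum schedule | Every-other-day repeats after first low value | Daily |
|---|---|---|---|
| 2 | 0% | 0% | 100% |
| 3 | 0% | 2/7 = 29% | 100% |
| 4 | 1/7 = 14% | 4/7 = 57% | 100% |
| 5 | 3/7 = 43% | 6/7 = 86% | 100% |
| 6 | 5/7 = 71% | 100% | 100% |
| 7 | 100% | 100% | 100% |

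The result is sensitive to how the 3- to 4-day interval is read. With gaps of 3 days throughout, 4-, 5- and 6-day episodes are caught in 1/3, 2/3 and all cases. With gaps of 4 days throughout, 4- to 7-day episodes are caught in 0, 1/4, 2/4 and 3/4 of cases.

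**Step 4. Patients already drawn every other day for Grade 4 neutropenia.** If that sampling covers the whole platelet episode, the shares are 0% at 2 days, 1/2 at 3 days and 100% from 4 days.

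**Step 5. Effect on the stopping rule (illustration).** Let b be the rate of other DLTs, q the rate of platelet episodes meeting the definition, and f the share detected. The recorded DLT rate is p = b + (1 − b)qf. For six evaluable patients, P(at least 2 DLTs) = 1 − (1 − p)⁶ − 6p(1 − p)⁵. All b and q values are assumptions; q = 6% borrows the adult Grade 4 rate.

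| b, q | f = 1 | f = 3/7 | f = 1/7 | f = 0 |
|---|---|---|---|---|
| 10%, 6% | 23% | 16% | 13% | 11% |
| 10%, 10% | 32% | 20% | 14% | 11% |
| 15%, 15% | 53% | 36% | 27% | 22% |

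For the first row at f = 1: p = 0.10 + 0.90 × 0.06 = 0.154, and 1 − 0.846⁶ − 6 × 0.154 × 0.846⁵ = 0.23. The table takes a full cohort of six; under the rolling six a level can be left earlier.

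**The case against.** **What stands and limits the size.**
- Twice-weekly draws put two counts in any 7-day window, so an episode lasting the full window is always seen. The gap concerns shorter episodes.
- Grade 4 neutropenia was common in adults (66%), and the CBC it triggers includes platelets. The gap therefore mainly affects thrombocytopenia without neutropenia, or outlasting it. The second case is plausible: Section 2.3.1 describes the Grade 4 neutropenia as lasting less than 5 days, and the extra draws stop at Grade 3.
- Transfusion on 2 separate days is another route to the DLT. But the documents give no transfusion threshold, and a single transfusion may lift the second count without meeting that route.
- Section 11.2.1 requires appropriate toxicity monitoring for DLT evaluability, and Section 14.3.2 provides weekly review. Both allow a query, but a patient on the minimum schedule would ordinarily count as evaluable without a DLT.
- The two criteria differ. Neutropenia lasting more than 7 days needs onset and recovery dated, which may explain why only neutropenia was singled out. That does not supply the second platelet count.

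**Stronger readings the documents do not support.**
- A reader might infer that the Day 18 test has no required value, because the next scheduled CBC could fall on Day 19, or on Day 22 in later cycles. Section 6.1.1.1 cannot be applied without a count by Day 18 in any cycle, so the recheck is implied. Only its absence from the evaluation table remains, a wording matter. Later cycles also lie outside the DLT period for escalation.
- A reader might multiply up the adult rate, 1 − 0.94⁶ = 31%, and take it as the share of six-patient cohorts affected. That is the chance of any Grade 4 thrombocytopenia at the adult rate. It is not the chance of a missed DLT, which also requires a qualifying short episode in Cycle 1, no second transfusion day and no extra CBCs.

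**Conclusion.** The concern holds in a limited form. The DLT definition and the Cycle 1 CBC schedule do not match for platelet episodes of about 2 to 6 days in patients without concurrent Grade 4 neutropenia and without transfusions on two days. At the minimum schedule such episodes are recorded as DLTs in 0% to 71% of cases, depending on length, against 100% with daily draws. Missing them lowers the recorded DLT rate and so leans towards escalation.

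The detection figures rest on random onset, alternating 3- and 4-day gaps and assumed durations. The effect on the stopping rule rests on assumed DLT rates and should be read as direction and rough scale only. The number of patients affected is probably small, given 6% Grade 4 thrombocytopenia in adults at 105 mg/m², although the planned levels of 125 and 150 mg/m² exceed the dose behind that figure. The point is worth correcting because it touches the primary endpoint and the correction is cheap.

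**What to change.** Reconcile Section 8.1 footnote 3 with Section 5.5.2.1 by stating which repeat CBC is required in Cycle 1 after a first platelet count below 20,000/mm³. One way is to extend the every-other-day rule already written for neutropenia to platelets, until recovery or DLT. This concerns ascertainment only; no DLT threshold or dose rule changes.

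The change reduces the dependence on draw frequency without removing it: 2-day episodes would still be missed, as would 71% of 3-day and 43% of 4-day episodes. If the sponsor wants classification to be independent of the site, the definition and the schedule have to be settled together. The evaluation table could also list the recheck by Day 18 that Section 6.1.1.1 implies.

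Cost: one clause in a footnote, a few extra CBCs in few patients, and possibly a slightly higher DLT count.

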#### 8.2 **Radiology Studies**

Patients who respond (CR, PR) to therapy or have long term stable disease (SD)  $(\geq 6 \text{ cycles})$  on protocol therapy will be centrally reviewed. COG Operations Center will notify the Imaging Center of any patient requiring central review. The Imaging Center will then request that the treating institution forward the requested images for central review. The central image evaluation results will be entered into RAVE for review by the COG Operations Center and for data analysis.

The images are to be forwarded electronically to the Imaging Research Center at Children's Hospital Los Angeles via the ImageInBox.

COG institutions that are not connected via the ImageInBox can send the images on CD ROM or USB flash drive. Submitted imaging studies should be clearly marked with the COG patient ID, study number (STUDY #ADVL1515) and date and shipped to [name] at the address below:

[name], CRP Administrator, Imaging Research Center Children's Hospital Los Angeles [name] [contact] [contact] E-mail: [contact]

#### 8.3 **Pharmacology**

Institute of the National Institutes of

This protocol is for research purposes only, see page 1 for usage policy

8.3.1 Description of Studies and Assay

Pharmacokinetics (PK) will be performed to determine the PK of LY2606368 in children. Plasma will be collected and LY2606368 concentrations will be determined by a validated LC/MS/MS method. Samples will be analyzed by Covance Laboratories.

### 8.3.2 Sampling Schedule (See Appendix V)

Blood samples will be obtained at the following time points:
Day 1: pre-dose, and at 1 (end of infusion), 1.5, 2, 4, and 8 hours after beginning the infusion.
Day 2: 24 hrs. (± 2 hrs.) after beginning the infusion.
Day 5 (± 1): 96 hrs. (± 24 hrs.) after beginning the infusion.
Day 8: During CBC evaluation
Day 15: pre-dose and end of infusion (1 hour after beginning the infusion).

### 8.3.3 Sample Collection and Handling Instructions

Blood samples (2 -3 ml) will be collected in  $K^2EDTA$  or  $K^3EDTA$  tubes at a site distant from the infusion for pharmacokinetic evaluation. Samples cannot be drawn from the  $2^{nd}$  lumen of a multi-lumen catheter through which drug is being administered. Record the exact time that the sample is drawn along with the exact start and stop time of the infusion.

### 8.3.4 Sample Processing

1. Invert the tube gently at least 8 to 10 times to ensure mixing of the KEDTA or KEDTA and blood.

2. Immediately after collection place  $K^2EDTA$  or  $K^3EDTA$  tube on ice or at 4°C for no longer than 30 minutes.

3. Centrifuge tube within 30 minutes of collection at 2000 g for 10 minutes at 4°C until red cells and plasma are well separated.

4. Transfer the plasma to cryovials. Do not transfer the buffy coat or any of the red cell pellet into the plasma sample as this will render the sample unusable for analysis.

5. Immediately after transfer of the plasma to cryovials, freeze the plasma samples on dry ice, snapfreeze in liquid nitrogen, or place directly into a -70°C freezer.
6. Store in -70°C freezer until shipment.

8.3.5 Sample Labeling

Each tube must be labeled with the patient's study registration number, the study I.D., and the date and time the sample was drawn. Data should be recorded on the Pharmacokinetic Study Form, which must accompany the sample(s).

### 8.3.6 Sample Shipping Instructions

Samples should be stored at -70°C until shipping, batched per patient and shipped frozen on dry ice in opaque containers at the end of Cycle 1. Shipments should only be sent out on Monday through Thursday via Fedex priority overnight to the following address:

Covance Bioanalytical Laboratory Services Inc. [name] Attn: Sample Management – Bioanalytical (Rm131D 1S) A program funded by the National Cancer Institute of the National Institutes of Health

Call the Covance Bioanalytical Services Sample Management department on the day prior to shipment ([name]), as notification of the intended shipment, or e-mail [contact] with shipment information (tracking numbers and number of boxes to be sent).

Please note the Covance study #8366627 for this study.

For further guidance, please see the sample shipping guidelines provided by Covance attached to the memo dated July  $4^{th}$  2017.

#### 8.4 **Tissue Studies (required)**

Archival tumor tissue should be submitted for all patients. If a patient does not have tissue available, the study chair must be notified prior to enrollment.

#### 8.4.1 Description of Studies

8.4.1.1 CHK 1/2 Expression

Tissue will be collected either from diagnosis or relapse to evaluate CHK1/2 expression in pediatric solid tumors prior to treatment with LY2606368. Tumor tissue will be analyzed by immunohistochemistry.

#### 8.4.1.2 TP53 Deletion/Mutation

Tissue will be collected either from diagnosis or relapse to evaluate for a deletion and/or mutation of *TP53* by immunohistochemistry and/or sequencing.

#### 8.4.2 Sample Collection, Handling, and Shipment

Paraffin-embedded tissue blocks or slides will be shipped to [name] at Phoenix Children's Hospital. Detailed instructions regarding collection, handling, and shipping of tissue samples are located in Appendix VI.

#### 8.4.3 Sample Labeling

Each sample must be labeled with the patient's study registration number, the study I.D., and the date and time the sample was taken. Data should be recorded on the Tissue Study Form, which must accompany the sample(s).

#### 8.5 **Correlative Biology Studies (optional)**

8.5.1 Description of Studies

Peripheral blood mononuclear cells (PBMCs) will be evaluated in consenting patients for autophosphorylation of Chk1 and H2AX using immunohistochemistry and/or phospho-flow cytometry.

#### 8.5.2 Sampling Schedule (See Appendix VII)

Blood samples (5 ml) will be collected at baseline prior to infusion and at 24 hours after start of infusion (at time of PK sample collection).

8.5.3 Sample Collection and Handling Instructions

nstitute of the National Institutes of Health

Blood samples (5 ml) will be collected in CPT tubes at a site distant from the infusion for pharmacodynamic evaluation. Record the exact time that the sample is drawn along with the exact time that the drug was administered.

#### 8.5.4 Sample Processing

Instructions for isolating PBMCs can be found in Appendix VIII. PBMCs should be kept on ice or refrigerated and processed within 1 hour of collection. Samples should be frozen standing upright in a rack or box to ensure that samples do not freeze to the sides and cap of the tube. Whenever possible, sites should use standard cryovials (i.e. volumes  $\leq 2.0$  mL) that can fit in a standard 81-place freezer box.

#### 8.5.5 Sample Labeling

Each tube must be labeled with the patient's study registration number, the study I.D., the date and time the sample was drawn, and the type of sample (either PMBC or plasma). Data should be recorded on the Correlative Study Form, which must accompany the sample(s).

#### 8.5.6 Sample Shipping Instructions

Samples should only be sent between Monday and Wednesday to ensure that sample shipments arrive at the lab during the work week. Please send an email confirmation prior to shipment to [contact] while copying the study specific research coordinator. This email should include the patient ID, tracking number, and the name of the shipping site.

Frozen samples may be batched and shipped together on dry ice to:

[figure not shown]

#### THIS PROTOCOL IS FOR RESEARCH PURPOSES ONLY, SEE PAGE 1 FOR USAGE POLICY

A program funded by the National Cancer Institute of the National Institutes of Health

#### 9.0 AGENT INFORMATION

THIS PROTOCOL IS FOR RESEARCH PURPOSES ONLY, SEE PAGE 1 FOR USAGE POLICY

9.1.6 9.1.7

A program funded by the National Cancer Institute of the National Institutes of Health This protocol is for research purposes only, see page 1 for usage policy  $% \left( {{{\rm{A}}} \right)$ 

A program funded by the National Cancer Institute of the National Institutes of Health

This protocol is for research purposes only, see page 1 for usage policy  $% \left( {{{\rm{A}}} \right)$ 

# 10.0 CRITERIA FOR REMOVAL FROM PROTOCOL THERAPY AND OFF STUDY CRITERIA

#### 10.1 Criteria for Removal from Protocol Therapy

- a) Clinical (including physical examination or serum tumor markers) or radiographic evidence of progressive disease (See Section 12.0).
- b) Adverse Events requiring removal from protocol therapy (See Section 13.0).
- c) Refusal of protocol therapy by patient/parent/guardian
- d) Non-compliance that in the opinion of the investigator does not allow for ongoing participation.
- e) Completion of 13 cycles of therapy.
- f) Physician determines it is not in the patient's best interest.
- g) Repeated eligibility laboratory studies (CBC with differential, bilirubin, ALT (SGPT) or serum creatinine) are outside the parameters required for eligibility prior to the start of LY2606368 (See Section 8.1).
- h) Study is terminated by Sponsor.
- i) Pregnancy

Patients who are removed from protocol therapy during cycle 1 should continue to have the required observations in Section 8.1 until the originally planned end of the cycle or until all adverse events have resolved per Section 13.4.4, whichever happens LATER. The only exception is with documentation of the patient's withdrawal of consent. Patients who are removed from protocol therapy in subsequent cycles should have the necessary observations to ensure adequate clinical care.

Patients who are off protocol therapy are to be followed until they meet the criteria for Off Study (see below). Ongoing adverse events, or adverse events that emerge after the patient is removed from protocol therapy, but within 30 days of the last dose of investigational agent, must be followed and reported via RAVE and CTEP-AERS (if applicable). Follow-up data will be required unless consent is withdrawn.

